Appendix 2. DATA DERIVATION DETAILS

Appendix 2.1. Definition and Use of Visit Windows in Reporting

Study visits are planned at Screening, Baseline and then at post-baseline Weeks 2, 4, 8, 16, 24, 32, 40, 48, 56, 64 and 80. If a subject discontinues from the trial then there will be an Early Termination Follow-Up period and for those who refuse, an Early termination visit. To account for this visit and any early or late scheduled visits (compared to the target study days) we define ‘windows’ to be able to allocate each efficacy observation to a single specific study visit. For the assessments made at study visits (eg, BPI-sf, PGA-LBP etc.) these visit windows are shown below. When multiple observations occur in a visit window, the observation closest to the protocol specified target day will be used, noting that the latter will be used in the case of a tie.

| Visit | Target Study Day | Window |
|---------------|---|--------------------------|
| Screening [1] | Variable (up to 30 days prior to baseline visit) | [No lower limit, Day -6] |
| Baseline | 1 (defined as initial day of study drug administration) | [-5,1] |
| Week 2 | 15 | [2,22] |
| Week 4 | 29 | [23,43] |
| Week 8 | 57 | [44,85] |
| Week 16 | 113 | [86,141] |
| Week 24 | 169 | [142,197] |
| Week 32 | 225 | [198, 253] |
| Week 40 | 281 | [254, 309] |
| Week 48 | 337 | [310, 365] |
| Week 56 | 393 | [366, 421] |
| Week 64 | 449 | [422, 477] |

As for BPI-sf, the visit window is below.

| Visit | Target Study Day | Window |
|---------------|---|--------------------------|
| Screening [1] | Variable (up to 30 days prior to baseline visit) | [No lower limit, Day -6] |
| Baseline | 1 (defined as initial day of study drug administration) | [-5,1] |
| Week 2 | 15 | [2,22] |
| Week 4 | 29 | [23,43] |
| Week 8 | 57 | [44,85] |
| Week 16 | 113 | [86,141] |
| Week 24 | 169 | [142,225] |
| Week 40 | 281 | [226, 309] |
| Week 48 | 337 | [310, 365] |
| Week 56 | 393 | [366, 421] |
| Week 64 | 449 | [422, 477] |

Besides the windows specified above, there is one additional window as defined as follows:

1. “16 Weeks after Last Dose”. This window will include data from 16 ± 4 weeks past the date of the last SC dose. The target day is 113 days after the last SC dose, with a window of [86, 141] days after the last SC dose. If multiple observations occur in this visit window, the observation closest to the specified target day will be used, noting that the latter will be used in the case of a tie.

EQ-5D-5L is collected at Baseline, Weeks 16 and 56, and ET1. WPAI:LBP is collected at Baseline, Weeks 16, 56, 64, and ET1 and ET2. HCRU is collected at Baseline, Weeks 64 and 80, and ET2 and ET3. TSQM and mPRTI are collected at Weeks 16 and 56, and ET1. The visit window for these visits will be defined below.

EQ-5D-5L, TSQM, mPRTI

| Visit | Target Study Day | Window |
|----------|---|-----------------------|
| Baseline | 1 (defined as initial day of study drug administration) | [-7, 1] |
| Week 16 | 113 | [2, 253] |
| Week 56 | 393 | [254, no upper limit] |

HCRU

| Visit | Target Study Day | Window |
|----------|---|-----------------------|
| Baseline | 1 (defined as initial day of study drug administration) | [no lower limit, 1] |
| Week 64 | 449 | [2,505] |
| Week 80 | 561 | [506, no upper limit] |

WPAI: OA,

| Visit | Target Study Day | Window |
|----------|---|-----------------------|
| Baseline | 1 (defined as initial day of study drug administration) | [no lower limit, 1] |
| Week 16 | 113 | [2,253] |
| Week 56 | 393 | [254, 421] |
| Week 64 | 449 | [422, no upper limit] |

Data in on-treatment analysis windows will be used in summaries and analyses of treatment period efficacy data, ie, up to Week 56, while data in off-treatment analysis windows will be only included in summaries (at Week 64, Week 80, 16 Weeks after Last Dose, and End of Study). Data in off-treatment analysis windows will be imputed, if needed, in analyses.

Any data collected up to 8 weeks (per the windowing rule above) from the last SC dose window is ‘on-treatment’, and any data collected more than 8 weeks (per the windowing rule above) after the last SC dose window is off treatment. For example, for patients whose last SC dose is at Week 8 (per the windowing rule above), any data collected after Week 16 (per the windowing rule above) will be off-treatment.

For the weekly diary average Low Back Pain Intensity scores, the data will be allocated to study weeks based on calendar weeks relative to the baseline visit (study day 1) and not based on the post-baseline visit schedule. The table below describes the visit days for each week. The mean of available weekly data in each of the weekly intervals will be used to calculate the weekly diary average Low Back Pain Intensity scores.

| Study Week | Days |
|------------|---------|
| 1 | 1-7 |
| 2 | 8-14 |
| 3 | 15-21 |
| 4 | 22-28 |
| 5 | 29-35 |
| 6 | 36-42 |
| 7 | 43-49 |
| 8 | 50-56 |
| 9 | 57-63 |
| 10 | 64-70 |
| 11 | 71-77 |
| 12 | 78-84 |
| 13 | 85-91 |
| 14 | 92-98 |
| 15 | 99-105 |
| 16 | 106-112 |

At the Screening visit only, the Low Back Pain Intensity (Numeric Rating Scale) will be administered with a patient worksheet for screening purposes. Also, the daily LBPI scores collected during the Initial Pain Assessment Period (Days-5 to -1), will be averaged to assess versus study inclusion criteria.

However, if a subject receives the Week 16 injection dose prior to Day 113, the Week 16 score will be calculated using the mean of the available scores from the 7 calendar days immediately prior to the Week 16 injection dose date. Any scores used in this calculation of Week 16 will not also be used in an earlier week calculation, eg, if the Week 16 dose occurs on Day 109, the available scores from Days 102-108 will be used to calculate the Week 16 score, and the available scores from Days 99-101 will be used to calculate the Week 15 score.

After the Week 16 visit, these are grouped in 4-week intervals using visit windows as shown below. If a subject comes in late for a Week 16 visit (or weekly diary is not activated at the visit), and so has daily diary data collected past Day 112, these data will be averaged with any data obtained weekly for any given interval.

All available on- or off-treatment data will be used for these windows after the planned treatment period.

| Summary Week | Includes Weeks | Days |
|--------------|----------------|---------|
| 20 | 17 - 20 | 113-140 |
| 24 | 21 - 24 | 141-168 |
| 28 | 25 - 28 | 169-196 |
| 32 | 29 - 32 | 197-224 |
| 36 | 33 - 36 | 225-252 |
| 40 | 37-40 | 253-280 |
| 44 | 41-44 | 281-308 |
| 48 | 45-48 | 309-336 |
| 52 | 49-52 | 337-364 |
| 56 | 53-56 | 365-392 |
| 60 | 57-60 | 393-420 |
| 64 | 61-64 | 421-448 |

When multiple observations occur in a day for pain score collected weekly, the average of scores will be used.

For rescue medication, data are collected until the end of study (Week 80 or final ET). Additional windows are defined below

| Summary Week | Includes Weeks | Days |
|--------------|----------------|---------|
| 68 | 65 - 68 | 449-476 |
| 72 | 69 - 72 | 477-504 |
| 76 | 73 - 76 | 505-532 |
| 80 | 77 - 80 | 533-560 |

Besides the windows specified above, there is one additional window as defined as follows:

“16 Weeks after Last Dose”. This window will include the average of all data collected from 13 to 16 calendar weeks (85 to 112 calendar days) past the date of the last SC dose. All available on- or off-treatment data will be used for this window after the planned treatment period.

Note that, similar to data collected at clinic visit, any data collected via diary up to 84 calendar day (12 weeks, 8 weeks + a 4 week window) from the date of the last SC dose are ‘on-treatment’, and any data collected more than 84 calendar day (12 weeks, 8 weeks + a 4 week window) from the date of the last SC dose are off treatment.

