In the event that a subject refuses the Early Termination safety follow-up or chooses to discontinue during the Safety Follow-up Period (after Week 56 of the study through Week 80), a complete early termination visit should be performed. This early termination visit should include all procedures scheduled for the Week 64 and Week 80 visits, unless Week 64 has already been completed; in that case, only Week 80 procedures will be required. In addition, if the Week 56 visit was not completed prior to termination, a general physical examination, TSQM, mPRTI will also be obtained. Subjects will be advised to continue their contraception regimen during a period of 112 days (16 weeks) after the last dose of SC investigational product.

Subjects entered in the Early Termination Follow-up Period will be able to take acetaminophen/paracetamol rescue medication daily up to the Early Termination Visit 2 that occurs 16 weeks after the last dose of investigational product, but will be advised not to exceed the maximum daily dose of 3000 mg. Subjects will be requested not to take acetaminophen/paracetamol (or any other analgesic) in the 24 hours that precede in-clinic visits at which efficacy assessments are collected (Up to and including Week 64 and Early Termination Follow-up period Visits 1 and 2, which occur 8 and 16 weeks after the last dose of SC investigational product, respectively). After the second Early Termination Follow-up visit occurring approximately 16 weeks after the last SC dose of investigational product, subjects may be started on standard of care treatments for low back pain. Subjects may continue to use acetaminophen/paracetamol as needed up to 3000 mg per day.

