7.2.8. Health Care Resource Utilization (HCRU)

The HCRU (eg, doctor office visits, hospitalizations, surgeries or procedures) during the 3 month period prior to Baseline will be collected by a questionnaire via IRT. In addition, HCRU will be collected at study visits at baseline, Week 64 and Week 80 (or at Early Termination, Visits 2 and 3).

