6.2.10. Health Care Resource Utilization (HCRU)

HCRU at Baseline, Weeks 64 and 80.

Individual items in HCRU at Baseline, Weeks 64 and 80 will be summarized as described in [Appendix 2.3](#). As for questions obtaining number of visits and number of nights stayed in the hospital, n, mean, median, standard deviation, minimum and maximum will be shown. As for questions obtaining binary or categorical responses, number and percentage of each response category will be shown.

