| Incidence of rescue medication use during Weeks 1, 2, 4, 8, 12, 16, 24, 32, 40, 48, 56 and 64 | ITT | None (summary) | NA | Observed Data | Secondary Endpoint Analysis |
| Number of days of rescue medication use during Weeks 1, 2, 4, 8, 12, 16, 24, 32, 40, 48, 56 and 64 | ITT | None (summary) | NA | Observed Data | Secondary Endpoint Analysis |
| Amount (mg) of rescue medication taken during Weeks 1, 2, 4, 8, 12, 16 | ITT | None (summary) | NA | Observed Data | Secondary Endpoint Analysis |
| Incidence of rescue medication use during Weeks 1, 2, 4, 8, 12, 16, 24, 32, 40, 48 and 56 | ITT | None (summary) | NA | LOCF | Secondary Endpoint Analysis |
| Number of days of rescue medication use during Weeks 1, 2, 4, 8, 12, 16, 24, 32, 40, 48 and 56 | ITT | None (summary) | NA | LOCF | Secondary Endpoint Analysis |

| | | | | | |
|--|-----|---------------------|----|---------------|-----------------------------|
| Amount (mg) of rescue medication taken during Weeks 1, 2, 4, 8, 12, 16 | ITT | None (summary) | NA | LOCF | Secondary Endpoint Analysis |
| Change from Baseline to Weeks 16, 56 and 64 in WPAI Impairment scores (Percent work time missed due to Low Back Pain; Percent impairment while working due to Low Back Pain; Percent overall work impairment due to Low Back Pain; Percent activity impairment due to Low Back Pain) | ITT | None (summary) | NA | Observed Data | Secondary Endpoint Analysis |
| EQ-5D dimensions (Mobility; Self-care; Usual activity; Pain/Discomfort; Anxiety/Depression) and Overall Health Utility at Baseline and Weeks 16 and 56 | ITT | Summary | NA | Observed Data | Secondary Endpoint Analysis |
| EQ-VAS at Baseline and Weeks 16 and 56 | ITT | Summary | NA | Observed Data | Secondary Endpoint Analysis |
| mPRTI endpoints (willingness to re-use; patient preference; patient satisfaction) at Weeks 16 and 56 | ITT | Summary | NA | Observed | Secondary Endpoint Analysis |
| TSQM endpoints (satisfaction with effectiveness, side effects and convenience, and overall satisfaction) at Weeks 16 and 56 | ITT | Summary | NA | Observed | Secondary Endpoint Analysis |
| Healthcare Resource Utilization at baseline, week 64 and 80 | ITT | Descriptive Summary | NA | Observed | Secondary Endpoint Analysis |

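### The SAP's HCRU windows report the 24-week early-termination visit as Week 64 for early terminators last dosed on schedule at Week 40 or earlier, and list no HCRU summary that uses their 16-week visit

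*SAP*

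**What the plan says.** - **Collection.** Protocol 7.2.8: "HCRU will be collected at study visits at baseline, Week 64 and Week 80 (or at Early Termination, Visits 2 and 3". SAP Appendix 2.1 agrees ("HCRU is collected at Baseline, Weeks 64 and 80, and ET2 and ET3") and introduces its windows as covering these visits.
- **Timing.** Protocol Table 2 puts ET2 at 16 weeks and ET3 at 24 weeks after the last SC dose, each ±7 days.
- **Windows.** The HCRU table in SAP Appendix 2.1 reads "Week 64 | 449 | [2,505": target Day 449, Days 2 to 505. Week 80 has target Day 561 and takes everything from Day 506.
- **Several records in one window.** SAP Appendix 2.1: "the observation closest to the protocol specified target day will be used", with the later record taken on a tie. The rule is not restated beside the HCRU table. No other rule in the appendix fits, since same-day averaging is given only for weekly pain scores.
- **Listed summaries.** SAP 6.2.10: "Individual items in HCRU at Baseline, Weeks 64 and 80 will be summarized". SAP Appendix 1: "Healthcare Resource Utilization at baseline, week 64 and 80", on observed data.
- **General off-treatment text.** Appendix 2.1 defines a further window by time since last dose ("This window will include data from 16 ± 4 weeks past the date of the last SC dose", Days 86 to 141 after that dose). After the HCRU and WPAI tables it confines off-treatment data to summaries at Week 64, Week 80, 16 weeks after last dose and end of study. It does not say whether the last two are produced for HCRU.
- **Single combined visit.** For a subject who refuses early-termination follow-up or leaves during safety follow-up, Protocol 6.9 says: "This early termination visit should include all procedures scheduled for the Week 64 and Week 80 visits". Only the Week 80 procedures are needed if Week 64 was already done.

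**The concern.** For collection, the protocol pairs ET2 with Week 64 and ET3 with Week 80. A window cut by study day, combined with a nearest-to-target rule, breaks that pairing. The Week 64 row would then join treatment completers seen 16 weeks after their last dose with early terminators seen 24 weeks after theirs.

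Protocol 6.9 allows standard-of-care treatment once ET2 is done. The retained ET3 record therefore follows eight weeks in which such care was permitted, though not necessarily used. Completers' Week 64 record precedes that permission. HCRU counts visits and services, so the row would describe two different situations under one label. It would be aligned neither to calendar time nor to time since last dose, and the Week 80 row would hold almost no early terminators.

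**Working it through.** **Reproducing the SAP's figures.** Target day = 7 × week + 1: 7 × 64 + 1 = 449 and 7 × 80 + 1 = 561. The midpoint is (449 + 561)/2 = 505, which is the stated cut.

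**Inputs.** Nominal SC dosing days are 1, 57, 113, 169, 225, 281 and 337. ET2 = last dose + 112 days. ET3 = last dose + 168 days. Of the records in Days 2 to 505, keep the one nearest Day 449, and the later on a tie.

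| Last dose | Day | ET2 day (distance) | ET3 day (distance) | Kept as Week 64 |
|---|---|---|---|---|
| Baseline | 1 | 113 (336) | 169 (280) | ET3 |
| Week 8 | 57 | 169 (280) | 225 (224) | ET3 |
| Week 16 | 113 | 225 (224) | 281 (168) | ET3 |
| Week 24 | 169 | 281 (168) | 337 (112) | ET3 |
| Week 32 | 225 | 337 (112) | 393 (56) | ET3 |
| Week 40 | 281 | 393 (56) | 449 (0) | ET3 |
| Week 48 | 337 | 449 (0) | 505 (56) | ET2 |

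**Visit windows.** Dose, ET2 and ET3 were each varied by ±7 days, with Day 1 fixed. ET3 was kept in all 225 combinations for Baseline and in all 3375 for each of Weeks 8 to 40. The closest case is a Week 40 dose on Day 288: the latest ET2 is Day 407 (distance 42) and the latest ET3 is Day 463 (distance 14). Day 463 is also the latest ET3 for any on-schedule last dose up to Week 40, so none reaches Day 506 and the Week 80 row.

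After a Week 48 dose, ET3 falls on Days 491 to 519. It passes Day 505, and so enters the Week 80 row, in 1575 of 3375 combinations. In the other 1800 both visits share the Week 64 window and ET2 is kept.

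**Delayed dose.** Protocol 7.4.3 allows dosing to resume up to 12 weeks after the previous dose. A Week 32 dose on Day 225 followed by a Week 40 dose on Day 225 + 84 = 309 is still inside the SAP's Week 40 window of Days 254 to 309. With ET2 seven days late, ET2 = 309 + 112 + 7 = 428 (distance 21) and ET3 = 309 + 168 = 477 (distance 28), so ET2 is kept. ET3 wins under every ±7-day combination of the ET visits only up to a last dose on Day 302.

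**Time since last dose.** ET2 falls at 105 to 119 days and completers' Week 64 at 98 to 126 days, both inside 86 to 141. ET3 falls at 161 to 175 days, outside it. Completers' Week 80 is 561 − 337 = 224 days, or 32 weeks.

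**Planning figures (Protocol 9.1).** The 30% responder rate at Week 16 is 60% from the osteoarthritis studies and 42% from the low back pain study. Non-responders are therefore 1 − 0.60 = 40% to 1 − 0.42 = 58%. They do not receive the Week 16 dose, so they were last dosed at Week 8 or earlier.

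**The case against.** The best defence is the general text in Appendix 2.1. ET2 and ET3 are off-treatment, and that text names a summary at 16 weeks after last dose, whose window holds ET2, and an end-of-study summary, which ET3 could fit. Among the clinic-visit window tables only HCRU has a Week 80 row, so the sentence plausibly reaches HCRU. The 16-week timepoint is also listed for no endpoint in SAP 6.2 or Appendix 1, so its absence for HCRU proves little. This stands in part. A reader might infer that ET2 is discarded, and the documents do not establish that. They establish only that no listed HCRU summary uses it. The general text does not undo the Week 64 labelling of ET3 either.

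A second defence is that the SAP windows by study day throughout, with similarly wide windows for EQ-5D-5L, TSQM, mPRTI and WPAI, and that Protocol 7.2.8 pairs the visits for collection, not for analysis. That is fair as to intent. But the kept record is not near Week 64 in calendar time either: after one dose it is Day 169.

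A reader might also see a conflict with Protocol 9.3, which excludes early-termination efficacy data more than 10 weeks after the last dose. The same section leaves HCRU reporting to the SAP, and the SAP windows these visits expressly, so this needs at most a clarifying line.

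**Conclusion.** The point holds as a minor labelling and alignment fault. For early terminators with both ET visits and an on-schedule last dose at Week 40 or earlier, the stated rules report ET3 as Week 64 and leave the Week 80 row empty. ET2 appears in no listed HCRU summary. The finding assumes that the nearest-to-target rule applies to HCRU, and it excludes markedly delayed doses.

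A reader might infer that treatment comparisons are distorted. They are not, because HCRU is summarised descriptively on observed data with no planned between-arm estimate.

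The number affected cannot be derived. The 40% to 58% of Week 16 non-responders indicates that the group could be large, but it assumes that rates from other studies apply to all three arms, celecoxib included. It also makes no allowance for attendance at ET2 and ET3, which the documents do not give.

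**What to change.** Assign HCRU by nominal follow-up visit:

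- ET2 goes with Week 64 in a row labelled as 16 weeks after last dose. ET3 goes with Week 80 in a row labelled as end of follow-up.
- The single combined visit of Protocol 6.9 goes in one row only: up to 141 days after last dose in the first row, later in the second. Footnote how many such records come before 86 days. Both limits are those of the SAP's own 16-week window. A visit with Week 80 procedures only goes in the second row.
- Treatment completers and early terminators are shown separately, or their counts footnoted.
- The SAP states whether the general 16-week and end-of-study summaries are produced for HCRU.

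As side clarifications, say that the 10-week exclusion in Protocol 9.3 does or does not apply to HCRU, and which recall period (3 months or 8 weeks, both mentioned in SAP Appendix 2.3) is used at each visit.

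The cost is a window-table edit and programming, with no new data. Rows are no longer calendar-aligned for early terminators (ET2 after one dose is Day 113), and the second row joins early terminators at 24 weeks with completers at 32 weeks after last dose. The separate display makes that visible.

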Appendix 2.2. Definition of Protocol Deviations that Relate to Statistical Analyses/Populations

Not applicable.

Appendix 2.3. Further Definition of Endpoints

Health State Utility of the EQ-5D-5L

The EQ-5D-5L contains five questions that measure the following dimensions: mobility, self-care, usual activities, pain/discomfort, and anxiety/depression. Each of the five dimensions has five levels: (1) no problems; (2), slight problems; (3) moderate problems; (4) severe problems; and (5) extreme problems.

The health utility scores are defined for every possible set of outcome combinations of the five dimensions for the following countries:

- Denmark, France, Germany, Japan, the Netherlands, Spain, Thailand, UK, US and Zimbabwe.

It is intended that this study will recruit patients from Japan.

WPAI:LBP Endpoints

The tables below summarizes the 6 questions of the WPAI:LBP questionnaire, and the four endpoints of the effect of impairment on activity and impairment.

| Question | Question Wording | Scoring |
|----------|---|---|
| 1 | Are you currently employed? [if No skip to question 6] | Yes, No |
| 2 | During the past seven days, how many hours did you miss from work due to problems associated with your Low Back Pain | number of hours (free text) |
| 3 | During the past seven days, how many hours did you miss from work because of any other reason, such as vacation, holidays, time off to participate in this study? | number of hours (free text) |
| 4 | During the past seven days, how many hours did you actually work (if '0' skip to Question 6) | number of hours (free text) |
| 5 | During the past seven days, how much did your Low Back Pain affect productivity while you were working? | 0 to 10 scale with 0 being 'Low Back Pain had no effect on my work' and 10 being 'Low Back Pain completely prevented me from working' |
| 6 | During the past seven days, how much did your Low Back Pain affect your ability to do your regular daily activities, other than work at a job? | 0 to 10 scale with 0 being 'Low Back Pain had no effect on my daily activities' and 10 being 'Low Back Pain completely prevented me from doing my daily activities' |

| | |
|---|--|
| WPAI endpoint | Calculation |
| Percent activity impairment due to Low Back Pain | $Q6*10$ |
| Percent impairment while working due to Low Back Pain | $Q5*10$ |
| Percent overall work impairment due to Low Back Pain | $\left\{ \frac{Q2}{Q2+Q4} + \left[1 - \left(\frac{Q2}{Q2+Q4} \right) \right] \left(\frac{Q5}{10} \right) \right\} \times 100$ |
| Percent work time missed due to Low Back Pain | $\frac{Q2}{Q2+Q4} * 100$ |

TSQM vII

The 11 questions of the TSQM and the scoring are shown below:

| Item | Question wording | Likert Scoring |
|------|---|---|
| 1 | How satisfied or dissatisfied are you with the ability of the medication to prevent or treat the condition? | 1 (Extremely dissatisfied) to 7 (Extremely satisfied) |
| 2 | How satisfied or dissatisfied are you with the way the medication relieves symptoms? | 1 (Extremely dissatisfied) to 7 (Extremely satisfied) |
| 3 | As a result of taking this medication, do you experience any side effects at all? | 0 (No), 1 (Yes) |
| 4 | How dissatisfied are you by side effects that interfere with your physical health and ability to function (eg, strength, energy levels)? | 1 (Extremely dissatisfied) to 5 (Not at all dissatisfied) |
| 5 | How dissatisfied are you by side effects that interfere with your mental function (eg, ability to think clearly, stay awake)? | 1 (Extremely dissatisfied) to 5 (Not at all dissatisfied) |
| 6 | How dissatisfied are you by side effects that interfere with your mood or emotions and ability to function (eg, anxiety/fear, sadness, irritation/anger)? | 1 (Extremely dissatisfied) to 5 (Not at all dissatisfied) |
| 7 | How satisfied or dissatisfied are you with how easy the medication is to use? | 1 (Extremely dissatisfied) to 7 (Extremely satisfied) |
| 8 | How satisfied or dissatisfied are you with how easy it is to plan when you will use the medication each time? | 1 (Extremely dissatisfied) to 7 (Extremely satisfied) |
| 9 | How satisfied or dissatisfied are you by how often you are expected to use/take the medication? | 1 (Extremely dissatisfied) to 7 (Extremely satisfied) |
| 10 | How satisfied are you that the good things about this medication outweigh the bad things? | 1 (Extremely dissatisfied) to 7 (Extremely satisfied) |
| 11 | Taking all things into account, how satisfied or dissatisfied are you with this medication? | 1 (Extremely dissatisfied) to 7 (Extremely satisfied) |

The scoring of the 4 satisfaction parameters are shown in the table below.

| TSQM Parameter | Scoring |
|---------------------|--|
| Effectiveness | $[(\text{Item 1} + \text{Item 2}) - 2] / 12 * 100$ |
| Side Effects | $[(\text{Item 4} + \text{Item 5} + \text{Item 6}) - 3] / 12 * 100$ If one item is missing then: $[(\text{Sum of two completed items}) - 2] / 8 * 100$ |
| Convenience | $[(\text{Item 7} + \text{Item 8} + \text{Item 9}) - 3] / 18 * 100$ If one item is missing then: $[(\text{Sum of two completed items}) - 2] / 12 * 100$ |
| Global Satisfaction | $[(\text{Item 10} + \text{Item 11}) - 2] / 12 * 100$ |

The four parameters have a scale of 0-100, with 100 being the best (most satisfied) score.

Healthcare Resource Utilization (example using 3 month recall – 8 week recall is also used in this study)

| Question | Response | Scoring |
|--|------------------|---|
| During the last 3 months, what services did you receive directly related to your low back pain? 
 • Primary Care Physician • Neurologist • Rheumatologist • Physician Assistant or Nurse Practitioner • Pain Specialist • Orthopedist • Physical Therapist • Chiropractor • Alternative Medicine or Therapy • Podiatrist • Nutritionist/Dietician • Radiologist • Home healthcare services • Other | Number of Visits | Response not selected = 0 Number of visits = 1-999 |
| During the last 3 months, have you visited the emergency room due to your low back pain? | Yes, No | No = 0 Yes = 1 |
| How many times? | Number of visits | 0-999 |
| During the last 3 months, have you been hospitalized due to your low back pain? | Yes, No | No = 0 Yes = 1 |
| How many nights in total did you stay in hospital due to your low | Number of Nights | 0-999 (max should be 92) |

| | | |
|--|--|--|
| back pain in the last 3 months? | | |
| 
Did you use these aids or devices to help you in doing things because of your low back pain in the last 3 months?
 
 • Walking Aid • Wheelchair • Devices or utensils to help you dress, eat or bathe • Other | 
Did not use any aids or devices Never, rarely, sometimes, often, always
 | 
Did not use any aids or devices = 0 Device not selected = 0 Never = 1 Rarely = 2 Sometimes = 3 Often = 4 Always = 5
 |
| 
Did you quit your job because of your low back pain?
 | 
Yes, No
 | 
No = 0 Yes = 1 Not applicable = 2
 |
| 
How long ago did you quit your job because of your low back pain?
 | 
Years and Months
 | 
0-99 Years and 0-99 Months (should be max of 11 months)
 |

Rescue Medication Endpoints

Rescue medication data is collected daily using an electronic system up to Week 16, and weekly after Week 16 and up to Week 64. Daily and Weekly collected data will be assigned to a specific study week for summary and reporting. The assignment of daily and weekly data to weeks will use the same principle as described above in [Appendix 2.1](#) for the weekly aLBPI data.

The incidence of rescue medication use will look for any incidence in the week of interest (collected through daily or weekly diary data). The number of days of RM use (using daily and weekly data) and the total amount taken (using daily data up to Week 16 only) over the week will be calculated for the assigned week algorithm described above.

Imputation is described in [Section 5.3](#) above. Imputation occurs for daily data up to Week 16 where the patient is in the trial and up to the end of that particular week.

An example of imputation and calculating the three endpoints using the daily diary data is shown below.

Example of calculating rescue medication data from Daily Diary Data (Patient does not discontinue)

In this example, a patient has a Week 2 visit on study day 14 (slightly earlier than the nominal day 15). Study days 8-14 would represent Week 2 data.

Using the Week 2 interval described above for a subject, ie, study days [8-14], we have the following rescue medication example data.

The amount taken and number of days of rescue medication use is adjusted for the duration of the Weekly interval.

| Study Day (Week) | Number of Doses of RM taken [1] | Number of Doses of RM taken [1] with LOCF imputation |
|------------------|---------------------------------|--|
| 8 (Week 2) | 2 | 2 |
| 9 (Week 2) | Missing | 2 [2] |
| 10 (Week 2) | 0 | 0 |
| 11 (Week 2) | 1 | 1 |
| 12 (Week 2) | Missing | 1 [2] |
| 13 (Week 2) | 2 | 2 |
| 14 (Week 2) | 0 | 0 |

[1] 500mg tablets of acetaminophen; [2] Using LOCF imputation for missing data

For this subject the following data will be calculated for Week 2:

- Incidence of rescue medication taken in Week 2: Yes. Rescue medication taken on days 8, 9 (imputed), 11, 12 (imputed), 13.
- Number of days of rescue medication use in Week 2: 5. For days 8-14 we have rescue medication taken on days 8, 9 (imputed), 11, 12 (imputed), and 13. The number of days taken for the 7 day period is $5/7*7=5$.
- Amount (mg) of rescue medication use in Week 2: For days 8-14 we have the number of doses taken of 2, 2 (imputed), 0, 1, 1 (imputed), 2, and 0. The number of doses taken for the 7 day period is $8/7*7=8$, making the amount of acetaminophen dosage of 4000 mg.

Example of calculating rescue medication data from Daily Diary Data (Patient discontinues)

In this example, a patient discontinues on study day 62, a few days after a Week 8 visit (which was on study day 60). The Week 5-8 data is calculated as described above (eg, Week 8 using days [50, 56]). The patient has rescue medication data as shown below.

| Study Day (Week) | Number of Doses of RM taken [1] | Number of Doses of RM taken [1] with LOCF imputation |
|------------------|---------------------------------|--|
| 57 (Week 9) | 1 | 1 |
| 58 (Week 9) | 1 | 1 |
| 59 (Week 9) | Missing | 1 [2] |
| 60 (Week 9) | Missing | 1 [2] |
| 61 (Week 9) | Missing | 1 [2] |
| 62 (Week 9) | Missing | 1 [2] |
| 63 (Week 9) | Missing | 1 [2] |

[1] 500mg tablets of acetaminophen; [2] Using LOCF imputation for missing data.

Week 9 is calculated as days 57 to 63. The data up to the end of the last week the patient was in the trial is imputed using LOCF as shown above. Therefore the Week 9 scores are then used to impute the Weekly data from summary and analysis for Weeks 10 to 56.

As above the incidence of rescue medication for Week 9 would be 'Yes'. The number of days of rescue medication use would be 7, and the average dose would be $7/7 * 7 * 500 = 3500$ mg for this week.

